## 2. INTRODUCTION

This statistical analysis plan (SAP) provides the detailed methodology for summary and statistical analyses of the data collected in Study C3421005. This document may modify the plans outlined in the protocol; however, any major modifications of the primary endpoint definition or its analysis will also be reflected in a protocol amendment.

### 2.1. Study Objectives, Endpoints, and Estimands

Objectives	Endpoints	Estimands
Primary:	Primary:	Primary:
To compare the effect of multiple dose levels of PF-06882961 versus placebo on glycated hemoglobin (HbA1c) in participants with type 2 diabetes mellitus (T2DM) on stable doses of metformin and/or diet and exercise.	Change from baseline in HbA1c at Week 16.	Estimand 1A: This estimand is intended to provide a population level estimate of the mean treatment effect (PF-06882961 versus placebo) on a continuous endpoint in participants on stable doses of metformin and/or diet and exercise without the benefit of glycemic rescue medication while on treatment.
Secondary:	Secondary:	Secondary:
To compare the effect of multiple dose levels of PF-06882961 versus placebo on glycemic control in participants with T2DM on stable doses of metformin and/or diet and exercise.	Response as defined by an HbA1c <7% at Week 16.	Estimand 2: This estimand is intended to provide a population level estimate of the odds ratio treatment effect (PF-06882961 versus placebo) on a binary responder endpoint in participants on stable doses of metformin and/or diet and exercise without the benefit of glycemic rescue medication.
	Change from baseline in HbA1c at Weeks 2, 4, 6, 8 and 12.	Estimand 1A as above.
	Change from baseline in fasting plasma glucose at Weeks, 2, 4, 6, 8, 12 and 16.	Estimand 3: This estimand will be the same as 1A.
To compare the effect of multiple dose levels of PF-06882961 versus placebo on body weight in participants with T2DM on stable doses of metformin and/or diet and exercise.	Change from baseline in body weight at Weeks 2, 4, 6, 8, 12 and 16.	Estimand 4: This estimand will be the same as 1A.
To characterize the safety and tolerability of multiple dose levels of PF-06882961 administered to participants with T2DM on stable	Incidence of treatment emergent adverse events [adverse events (AEs) and serious adverse events (SAEs)], clinical laboratory abnormalities, vital signs (blood pressure and pulse rate) and electrocardiogram (ECG)	There are no defined estimands for these endpoints and they will be analyzed using Pfizer data standards as applicable.

doses of metformin and/or diet and exercise.	parameters (heart rate, QT, QTcF, PR and QRS intervals).	
CCI [REDACTED]	[REDACTED]	[REDACTED]
[REDACTED]	[REDACTED]	[REDACTED]
[REDACTED]	[REDACTED]	[REDACTED]
[REDACTED]	[REDACTED]	[REDACTED]
[REDACTED]	[REDACTED]	[REDACTED]
CCI [REDACTED]	[REDACTED]	[REDACTED]
[REDACTED]	[REDACTED]	[REDACTED]
[REDACTED]	[REDACTED]	[REDACTED]

[REDACTED]

CCI		
For all endpoints, baseline is defined as the result closest prior to dosing at Visit 3 (Day 1).		

### 2.1.1. Primary Estimand(s)

The primary estimand (Estimand 1A) will be the population average treatment effect on the change from baseline in HbA1c at Week 16 of PF-06882961 compared to placebo in the absence of glycemic rescue medication while on treatment and stable doses of background metformin and/or diet and exercise. This reflects a combination of the 'Hypothetical' and 'While on treatment' strategies as outlined in the ICH-E9 (R1) draft guidance (1). It includes the following 4 attributes:

- Population: Defined by the inclusion and exclusion criteria to reflect participants with T2DM who are on a background of metformin and/or diet & exercise
- Variable: Change from baseline in HbA1c (%) at Week 16
- Intercurrent events: All data after an intercurrent event of glycemic rescue medication and/or discontinuation of investigational product (IP) will be censored
- Population-level summary: Difference of variable means between PF-06882961 (each dose considered separately) and placebo

### 2.1.2. Secondary Estimand(s)

#### 2.1.2.1. Estimand Related to Achieving HbA1c <7% at Week 16

A secondary estimand (Estimand 2) will be the population odds ratio of the treatment effect of achieving HbA1c <7% at Week 16 of PF-06882961 compared to placebo in the absence of glycemic rescue medication in participants while on treatment and on stable doses of background metformin and/or diet and exercise. This reflects a combination of the 'Hypothetical' and 'While on treatment' strategies as outlined in the ICH-E9 (R1) draft guidance (1). It includes the following 4 attributes:

- Population: Defined by the inclusion and exclusion criteria to reflect participants with T2DM who are on a background of metformin and/or diet & exercise
- Variable: Response as defined by an HbA1c <7% at Week 16
- Intercurrent events: Any participant with an intercurrent event of glycemic rescue medication and/or discontinuation of IP prior to Week 16 will have all subsequent data

censored if not missing. Missing or censored values at Week 16 will be imputed (assuming missing at random [MAR]) to determine a response classification.

- Population-level summary: Odds ratio for a response between PF-06882961 (each dose considered separately) and placebo

#### 2.1.2.2. Estimands Related to Fasting Plasma Glucose and Body Weight

These estimands (Estimands 3 and 4) will utilize the same approach as Estimand 1A (Section 2.1.1) for the associated endpoint(s).

CCI

[Redacted text block]

[Redacted text block]

[Redacted text block]

[Redacted text block]

[Redacted text block]

[Redacted text block]

## 2.2. Study Design

[figure not shown]
*This Phase 2b, multi-center, randomized, double-blind, placebo-controlled, 6 - arm, parallel group, study will assess efficacy and safety of twice daily administration of PF-06882961 in adult participants with T2DM inadequately controlled on metformin monotherapy or diet and exercise alone. At least 80% of the enrolled participants are required to be on metformin prior to screening.*

[Redacted text block]

Following the screening period to confirm eligibility (up to 4-weeks), the study will consist of a 2-week placebo run-in period, prior to randomization on Day 1. The treatment period will be 16 weeks, followed by an approximate 4-week follow-up. The total duration of participation in this study is approximately 22 weeks, not including the screening period.

Participants will be randomized to one of the following 6 treatment arms (in a 1:1:1:1:1:1 ratio): placebo, 2.5 mg BID, 10 mg BID, 40 mg BID, 80 mg BID or 120 mg BID. Dosing will occur with food twice daily, and up to 6 weeks of the 16-week dosing duration will be used for dose titration to maximize tolerability of PF-06882961.

Approximately 400 participants (approximately 67 participants per treatment arm) will be randomized to ensure completion of approximately 300 participants (approximately 50 participants per treatment arm). Randomization will be stratified according to background diabetes treatment (presence or absence of metformin therapy).

### 3. ENDPOINTS AND BASELINE VARIABLES: DEFINITIONS AND CONVENTIONS

Baseline is defined as the result closest prior to dosing at Visit 3 (Day 1) for all endpoints.

### 3.1. Primary Endpoint(s)

The primary efficacy endpoint is the change from baseline in HbA1c at Week 16.

### 3.2. Secondary Endpoint(s)

- Response as defined by an HbA1c <7% at Week 16

This endpoint will have two levels: ‘Response’ and ‘Non-response’. The former will be based on participants having an HbA1c < 7% at Week 16, otherwise participants with a value  $\geq 7\%$  will be classed as having a ‘Non-response’. Participants with an intercurrent event of starting glycemc rescue medication and/or discontinuation of IP prior to Week 16 will have all subsequent data censored if not missing. If glycemc rescue medication and/or discontinuation of IP occurs at Week 16, the data will not be censored. The intercurrent event that occurs first during the study will take precedence for determining the censoring of data. Missing or censored values at Week 16 will be imputed as described in Section 5.3.

- Change from baseline in HbA1c at Weeks 2, 4, 6, 8 and 12
- Change from baseline in fasting plasma glucose at Weeks 2, 4, 6, 8, 12 and 16
- Change from baseline in body weight at Weeks 2, 4, 6, 8, 12 and 16

The average of the duplicate body weight readings collected at each assessment time will be calculated prior to summaries/analysis. If one of the two duplicates are missing, the non-missing value will be used, and missing values will not be imputed. Both the absolute change and %change from baseline in body weight will be calculated.

CCI

[REDACTED]

CCI [REDACTED]

[REDACTED]

### 3.4. Baseline Variables

Baseline measures will be included as a covariate in all applicable statistical models along with the stratification variable of whether or not a participant was on background metformin at screening (see Section 4.1).

The statistician may conduct further exploratory analyses into the effect of covariates and factors (such as gender, age and strata) on the efficacy endpoints. If conducted, and considered relevant to the clinical study report (CSR), the methods will be fully justified and discussed within the report.

### 3.5. Safety Endpoints

#### 3.5.1. Adverse Events

An adverse event is considered treatment emergent (TEAE) relative to a given treatment if:

- the event starts during the effective duration of treatment (i.e. starting on or after the first dose but before the last dose plus lag time)

The effective duration of treatment is determined by the lag time. Any event occurring within the lag time, whether this occurs during a break in treatment or at the end of treatment, is attributed to the corresponding treatment period. The lag time is defined by the Pfizer Standard of 365 days post last dose of IP.

Adverse events occurring during the placebo run-in period (i.e. starting from Day -14, inclusive, up to and before the first dose of active treatment on Day 1) will be considered non-treatment emergent.

A 3-tier approach will be used to summarize TEAEs. Under this approach, TEAEs are classified into 1 of 3 tiers. Different analyses will be performed for different tiers (see Section 6.6.1).

Tier 1 events: These are prespecified events of clinical importance and are maintained in a list in the product's Safety Review Plan (or similar, e.g. Safety Surveillance Review Plan).

Tier 2 events: These are events that are not tier 1 but are "common." A Medical Dictionary for Regulatory Activities (MedDRA) preferred term (PT) is defined as a Tier 2 event if there are at least 5% of participants reporting the event in any treatment group.

[REDACTED]

Tier 3 events: These are events that are neither Tier 1 nor Tier 2 events.

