### **3.5.1.1. Subset Reporting Interval**

A summary of adverse events occurring during a subset of the main reporting interval will be based on a shorter reporting window. This will include all TEAEs starting after or on the first dose, but doesn't start more than two days after the last dose of IP (defined as either completing the 16 weeks of treatment or discontinuing from IP earlier).

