## 6. ANALYSES AND SUMMARIES

Data collected before baseline will only be listed, unless otherwise stated.

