#### **6.6.1. Adverse Events**

Adverse events (Tier 1, 2 and 3 AEs as described in Section 3.5.1) will be summarized by treatment and overall and in accordance with sponsor reporting standards using the safety analysis set defined in Section 4. The adverse events (AEs) will be sorted in descending frequency within a system organ class.

Incidence and severity of treatment emergent adverse event (TEAE) tables will additionally be produced ('All causality' and 'Treatment related', separately) to summarise the total number of adverse events by preferred term, which will be reported by treatment and overall.

The following tables and figures related to TEAEs classed as Tier 1 or 2 will be ordered in descending point estimate of risk difference within System Organ Class. If two or more events have the same frequency they will be sorted alphabetically by preferred term.

TEAEs classed as Tier 1 events will be tabulated by treatment. Number of participants and percent will be presented, along with the risk difference between each dose of PF-06882961 and placebo. 95% confidence intervals and 2-sided p-values will also be presented for the comparison. No adjustment for multiplicity will be used.

Tier 1 TEAEs will also be presented graphically. The TEAEs will be presented in a two-panel plot, the left panel will give the proportions of TEAEs observed in a dose of PF-06882961 and separately placebo while the right panel will display the 95% confidence interval for the risk differences for each TEAE. A vertical line corresponding to the value of 0 will be added to the right-hand plot. For the graphical display for tier 1 events, a column containing the 2-sided p-value for each event will be added to the right-hand side of the forest plot in the right panel. Each panel will be paged by dose of PF-06882961.

TEAEs classed as Tier 2 events will be summarised and graphically presented similar to Tier 1 events, but no p-values will be presented. No adjustments for multiplicity will also be used.

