For Tier 1 and Tier 2 outputs, footnotes will be included on the tables to provide proper interpretation of p-values (Tier 1 only) and confidence intervals and to describe how the comparison was conducted, e.g. “P-values and confidence intervals are not adjusted for multiplicity and should be used for screening purpose only. 95% Confidence intervals are provided to help gauge the precision of the estimates for Risk Difference. Risk Difference is computed as PF-06882961 versus placebo.”

It should be recognized that most studies are not designed to reliably demonstrate a causal relationship between the use of a pharmaceutical product and an adverse event or a group of adverse events. Except for select events in unique situations, studies do not employ formal adjudication procedures for the purpose of event classification. As such, safety analysis is generally considered as an exploratory analysis and its purpose is to generate hypotheses for further investigation. The 3-tier approach facilitates this exploratory analysis.

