### **6.6.1.4. Percentage of Participants with Ongoing AEs of Interest**

Exploratory summaries on the percentage of participants reporting AEs of interest will be produced by week and treatment and overall as per Section 5.2.2 from Week 1 up to Week 18 (i.e. including the follow-up visit 10).

To calculate the percentage each week, the total number of participants who experience the TEAE of interest at any time during the respective week will be the numerator and the total number of participants who had not discontinued from IP and/or the study prior to that respective week will be the denominator (note if a participant did discontinue from IP and/or the study during that respective week they would be included in the denominator).

A line plot of the percentages over each week will be produced based on the summary statistics with a separate line for each treatment.

The AEs of interest are diarrhoea, nausea and vomiting (based on preferred term); where a separate table and plot will be produced for each AE.

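### SAP 3.5.1 defines a TEAE by start date only and has no rule for an AE open at Day 1 that worsens on treatment

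*SAP*

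**What the plan says.** SAP 3.5.1 lists one criterion for a TEAE: "the event starts during the effective duration of treatment (i.e. starting on or after the first dose but before the last dose plus lag time". Here the lag time is 365 days after the last dose. The same section says that events in the placebo run-in "will be considered non-treatment emergent", and it makes no exception for later worsening. Events that start in screening, before the run-in, are excluded by the start-date criterion itself. The one redaction visible in this section follows the Tier 2 text, so nothing suggests that a worsening criterion was blacked out.

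Several outputs inherit the definition:

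- SAP 3.5.1.1, the shorter reporting window: "This will include all TEAEs starting after or on the first dose".
- SAP 6.6.1: "Incidence and severity of treatment emergent adverse event (TEAE) tables will additionally be produced". The Tier 1 and Tier 2 displays are also built from TEAEs, and a preferred term "is defined as a Tier 2 event if there are at least 5% of participants reporting the event in any treatment group".
- SAP 6.6.1.4, the weekly display of ongoing events: "the total number of participants who experience the TEAE of interest at any time during the respective week will be the numerator".

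On the collection side, Protocol 8.3.1 starts active AE collection at informed consent, and Protocol 8.3.1.2 puts those events on the AE section of the CRF. Screening lasts up to 4 weeks and the run-in 2 weeks (Protocol 4.1), so a record can be opened up to about 6 weeks before first dose.

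**The concern.** TEAE incidence is a secondary endpoint of a study meant to support dose selection. Under a start-date rule alone, the same clinical course may or may not be a TEAE, depending on how the site enters it. Suppose mild nausea begins in the run-in, is still open at Day 1 and becomes severe during titration. If the site opens a new record, this is a severe on-treatment TEAE. If the site raises the severity on the existing record, it is a non-treatment-emergent event.

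In the second case the worsening is missing from the TEAE incidence and severity tables, the Tier 1 and Tier 2 displays, the subset-interval tables and the weekly numerator. The SAP promises no by-arm display of on-treatment worsening that would recover it. Incidence and severity could then be understated in any arm, placebo included.

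**Working it through.** The plan states no figure to reproduce. The check is a comparison of texts, followed by arithmetic for scale.

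**Text comparison: an AE with onset after consent, open at Day 1, that worsens on treatment**

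| Route | Support in the documents | Start date held | TEAE under SAP 3.5.1? |
|---|---|---|---|
| Worsening entered as a new AE | Protocol 10.3.1: an exacerbation is itself an AE | On or after first dose | Yes |
| Severity updated on the open record | Protocol 10.3.3, follow-up: updates go to the CRF first completed (a general bullet that does not mention severity) | Before first dose | No |

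Neither document chooses between the routes. Protocol 10.3.3 asks for one intensity category per event and mentions no date of change. The CRF is not among the documents, so an updated record may or may not show when the worsening happened.

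Displays not worded as TEAE-only are not necessarily affected: discontinuations (SAP 6.5.6), time to first occurrence (6.6.1.3) and time to GI discontinuation (6.6.1.5). The same holds for SAE reporting.

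**Inputs for scale**

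- About 67 participants per arm (Protocol 9.2), so 5 × 67 = 335 on active treatment.
- Tier 2 threshold of 5% in any arm (SAP 3.5.1).
- Nausea at 49.0% in C3421002 (Protocol 2.2.2.1). This matches 48/98, all participants with placebo included. Using 49% as the active rate, and 5% to 20% on placebo, is therefore an assumption.

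**Per missed participant**

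- One arm: 1/67 = 1.49 points.
- Active arms pooled: 1/335 = 0.30 points.

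**Tier 2 boundary**

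- 0.05 × 67 = 3.35, so 4 participants are needed: 4/67 = 5.97%, against 3/67 = 4.48%.
- One missed participant can move a term from Tier 2 to Tier 3 only if that arm sits exactly at 4 and no other arm reaches 5%.

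**Common GI term**

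SE of the risk difference = √(0.49 × 0.51/67 + q(1 − q)/67), where q is the placebo rate. Net missed participants for a shift of 1 SE = SE × 67.

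| q | SE (points) | Net missed on active for 1 SE |
|---|---|---|
| 5% | 6.66 | 4.5, so 5 |
| 10% | 7.12 | 4.8, so 5 |
| 20% | 7.82 | 5.2, so 6 |

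One net missed participant is 1.49/7.82 = 0.19 to 1.49/6.66 = 0.22 SE. A net excess of 5 or 6 on active is unlikely, because a participant with any new on-treatment episode of the term already counts towards incidence.

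**Uncommon term (illustration only; the SAP plans no such bound)**

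The exact one-sided 95% upper bound is 6.89% for 1/67. For 0/67 it is 1 − 0.05^(1/67) = 4.37%. This shows what losing any single event does, whatever the cause.

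**The case against.** The strongest reply is that the ordinary route already captures worsening. Protocol 10.3.1 covers exacerbated as well as new conditions, and clinically significant results that worsen from baseline. A site following it would enter an on-treatment exacerbation as an AE with an on-treatment start. The Protocol 10.3.3 bullet sits among general follow-up instructions, may mean the CRF as a whole, and does not tell anyone to overwrite a severity. This stands: many such worsenings will count, and no instruction in the documents produces the error.

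Second, the deciding rule may lie outside these documents. Protocol 3 and 9.4.2 defer safety reporting to the sponsor's data standards, and SAP 6.6.1 defers to sponsor reporting standards. CRF guidance may already require a new record. SAP version 2 also made minor edits to 3.5.1 after blinded data review, though the change log does not say whether worsening was considered. This too stands, and citing such a rule would largely close the point.

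Third, the exposed group is narrow. A condition that predates consent has no open AE record to update. What remains is an event that begins between consent and Day 1, stays open, worsens on treatment and is updated rather than re-entered. For incidence, the participant must also have no other episode of that term. The documents give no rate for any step.

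Fourth, the SAP says "safety analysis is generally considered as an exploratory analysis", and Tier 3 events are still summarised by treatment, so a tier crossing costs the risk-difference display and not the event.

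Two stronger readings are tempting, and neither is supported. A reader might infer that the risk differences are biased. That needs such worsening to be missed at different rates by arm, which nothing in the documents shows. A reader might also infer from SAP 6 ("Data collected before baseline will only be listed, unless otherwise stated") that worsened events are deliberately reduced to listings. That sentence concerns data collected before baseline and does not govern an update made after Day 1.

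None of this supplies the missing criterion. The rule as written can still misclassify a worsening held on its original record.

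**Conclusion.** The gap is real but minor. SAP 3.5.1 classifies by start date alone, and an AE open at Day 1 whose worsening is held on its original record falls outside every TEAE output. The total effect cannot be derived from the documents. It is probably small: 1.5 points per missed participant in an arm, little movement for common GI terms, and relatively more for uncommon ones. It touches the completeness of an exploratory safety description. No formal test is affected.

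The conclusion assumes that some sites update open records rather than re-enter them, and that no unseen CRF or sponsor rule forbids it. If such a rule exists, little is left beyond making the SAP wording explicit.

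**What to change.** 1. Add to SAP 3.5.1: *An AE with onset before first dose is also treatment emergent if its severity increases, or it becomes serious, on or after first dose and within the lag time; the date of worsening is used as onset.*
2. Make the rule workable in the data. Either confirm, and cite, that CRF guidance requires a new record with its own start date for such worsening, or query the AEs open at Day 1 for post-dose worsening before unblinding. The SAP sentence alone cannot be applied where a record holds one undated severity.

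The cost is one SAP sentence, plus either a reference to existing guidance or one set of queries. The downside is slightly higher TEAE counts and a small data-management check.
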